5.2.4. Data Handling

Subjects who meet treatment failure criteria specified in Section 5.1.3.2 or rescue treatment criteria in Section 5.1.3.4 prior to Week 16 will be considered not to have achieved an IGA score of cleared (0) or minimal (1) or a PASI 75 response at Week 16. In addition, subjects with a missing IGA or PASI score at Week 16 or who do not return for evaluation at Week 16 will be considered not to have achieved the respective endpoint at Week 16.

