### **6.5.1. Rescue Medication**

In Part 1 of the study, participants with a PASI score increase of  $\geq 50\%$  from their baseline PASI score at Week 8 or Week 12 will be allowed to use a topical steroid as rescue treatment, with the exception of ultra-high potency topical steroids (eg, clobetasol propionate, halobetasol propionate) which are not allowed at any time. It is recommended that participants use no more than 60 grams of topical steroid per week. In addition, participants should be managed using the lowest possible potency and frequency of rescue topical steroid. Participants must discontinue the use of rescue topical steroids by Week 20 (should not initiate rescue topical steroids at or after Week 16).

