#### **9.4.1.3. Primary Analysis**

There are 2 primary estimands corresponding to the 2 co-primary endpoints in this study for participants randomized in Part 1 of this study: the proportion of participants who achieve an IGA score of cleared (0) or minimal (1) and the proportion of participants who achieve a PASI 75 response at Week 16. These 2 co-primary endpoints will be compared between the guselkumab group and the placebo group. In the primary efficacy analysis, data from all randomized participants will be analyzed according to their assigned treatment group. Participants who meet treatment failure criteria or initiate use with a low to high potency topical steroid as rescue treatment before Week 16 will be considered nonresponders for the primary endpoints at Week 16. In addition, participants who do not return for evaluation at Week 16 will be considered nonresponders at Week 16.

To address the primary objective, a 2-sided ( $\alpha=0.05$ ) Fisher's exact test, stratified by age and region, will be used for the co-primary endpoints. The exact 95% confidence interval for treatment difference between guselkumab and placebo treatment groups will be provided.

The study will be considered positive if the guselkumab group is significantly different from the placebo group for both co-primary endpoints. If one of the comparisons is not significant at the 2-sided  $\alpha$ -level of 0.05, the co-primary endpoints will be considered not significant.

In addition, the comparison between etanercept and placebo for the co-primary endpoints will be performed and nominal p-values will be reported.

Subgroup analyses will be performed to evaluate consistency of the co-primary endpoints over demographics (including baseline weight), baseline disease characteristics and prior medications. Sensitivity analyses and per-protocol analysis will be performed for the co-primary endpoints and will be documented in the SAP.

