5.1.3.4. Rescue Treatment

In Part 1 of the study, participants with a PASI score increase of $\geq 50\%$ from their baseline PASI score at Week 8 or Week 12 will be allowed to use a topical steroid as rescue treatment up until Week 16, with the exception of ultra-high potency topical steroids (eg, clobetasol propionate, halobetasol propionate) which are not allowed at any time. It is recommended that participants use no more than 60 grams of topical steroids per week. In addition, participants should be managed using the lowest possible potency and frequency of rescue topical steroid. Participants must discontinue the use of rescue topical steroids by Week 20.

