5.1.3.5. Rescue Treatment Rules

Subjects who use a low to high potency topical steroid starting at Week 8 or Week 12 as a result of being eligible for rescue treatment will be considered as nonresponders for binary endpoints and zero (no change from baseline) will be assigned to continuous outcomes from that point onward through Week 16. The analysis at and after Week 20 will use the observed data without imputation. Treatment failure rules will be applied if subjects continue to use or initiate treatment of a low to high potency topical steroid after Week 20.

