5.3.2.2. Estimands for Continuous Endpoint of CDLQI

5.3.2.2.1. Composite Strategy

The composite strategy assesses the treatment effects not only based on the variable measurements, but also based on intercurrent events defined in TF and rescue treatment criteria.

Population: subjects with chronic plaque psoriasis who are randomized to guselkumab or placebo in Part 1 of the study.

Variable: the endpoint is defined as the change from baseline in CDLQI at Week 16. Zero change is assigned after a subject meet TF or rescue treatment criteria.

Intercurrent Events: the intercurrent event is captured through the variable definition.

Population-level summary: difference in LSmean between guselkumab group and placebo group.

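### SAP 5.2.4 and three estimand definitions trigger failure on eligibility for rescue, not on its use; CDLQI is the result that could change

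*SAP*

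**What the plan says.** The SAP states two triggers for the same outcome.

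*Eligibility.* SAP 5.2.4 denies a Week 16 response to participants who meet treatment failure criteria "or rescue treatment criteria in Section 5.1.3.4 prior to Week 16 will be considered not to have achieved" it. Section 5.1.3.4 lists one entry condition, a PASI at least 50% above baseline at Week 8 or Week 12, and says that such participants "will be allowed to use a topical steroid as rescue treatment up until Week 16". That is permission; the section assigns no outcome. The Variable lines of 5.2.2 (co-primary) and 5.3.2.1 (binary major secondary) also refer to meeting rescue criteria. For CDLQI, 5.3.2.2.1 reads: "Zero change is assigned after a subject meet TF or rescue treatment criteria". Section 5.3.4 carries the handling in 5.2.4 over to the major secondary analyses.

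*Use.* SAP 5.1.3.5 covers "Subjects who use a low to high potency topical steroid starting at Week 8 or Week 12" because they qualified for rescue. It assigns non-response to binary endpoints and zero change to continuous ones through Week 16. Protocol 9.4.1.3 says that participants who "initiate use with a low to high potency topical steroid as rescue treatment before Week 16 will be considered nonresponders" for the primary endpoints. The narrative of SAP 5.2.2 speaks of having to use rescue medication. The per-protocol definition (2.4.1.2) and both co-primary sensitivity analyses (5.2.5) cite 5.1.3.5.

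Section 5.2.2 therefore contains both versions.

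**The concern.** Rescue is optional, so eligibility and use are different events. A participant who qualifies and takes no steroid has had no intercurrent event of rescue. Under 5.2.4 and the Variable lines the outcome is still overwritten; under 5.1.3.5 the observed value stands. For endpoints in the confirmatory sequence, the definition should not depend on which section the programmer follows.

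There is also a consequence for the co-primary sensitivity analyses. They are meant to vary the handling of missing data. Read literally, they change the rescue trigger as well, because the primary analysis cites 5.1.3.4 and they cite 5.1.3.5.

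**Working it through.** 1. **Who is classified differently at Week 16.** Eligible and used rescue: overwritten under both triggers. Not eligible, no steroid: under neither. Not eligible but used a topical steroid for psoriasis: a treatment failure under SAP 5.1.3.2 in either case. Eligible, no steroid: overwritten under the eligibility trigger only. This last group is the only one that matters. The documents give no rate for it.

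2. **The plan's own power figure.** Inputs from SAP 1.4: 65% v 13%, n = 40 v 25, two-sided 0.05, stated power >99%. Full enumeration of the two binomials with an unstratified Fisher's exact test gives 99.3% at 65%, 99.8% at 70%, and above 99.9% at 75% and 85%. For etanercept it gives 81.0%, 84.9% and 92.4% against the stated 81%, 85% and 92%. All figures reproduce. None carries a term for rescue, so none depends on the trigger.

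3. **What an eligible non-user needs in order to respond.** Eligibility means PASI of at least 150% of baseline at Week 8 or 12. PASI 75 means at most 25% of baseline at Week 16. The required fall is 1 − 25/150 = 83.3% within 4 to 8 weeks without rescue. For PASI 90 it is 1 − 10/150 = 93.3%; for PASI 100 it is complete clearance. At the minimum entry PASI of 12 (inclusion criterion 2), PASI 75 means going from at least 18 to at most 3. Anyone who falls short is a PASI non-responder under both triggers. For IGA 0/1 there is no such formula, but the same course would be needed clinically.

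4. **Size if it happened all the same.** Each recoded responder costs 1/40 = 2.5 points on guselkumab or 1/25 = 4 points on placebo. Take planning counts of 26/40 (65%) and 3/25 (13% of 25 is 3.25, rounded). Unstratified Fisher p-values:

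| Recoded (assumed) | Counts | Difference | p |
|---|---|---|---|
| none | 26/40 v 3/25 | 53.0 points | 0.00003 |
| 3 on guselkumab | 23/40 v 3/25 | 45.5 points | 0.0003 |
| 3 on placebo | 26/40 v 0/25 | 65.0 points | <0.00001 |

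5. **CDLQI.** A higher score is worse, so a positive change c is a worsening. Setting c to zero moves the raw arm mean by −c/25 on placebo or −c/40 on guselkumab. The values of c are assumed:

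| c | placebo, 1 participant | placebo, 3 participants | guselkumab, 1 participant |
|---|---|---|---|
| 2 | −0.08 | −0.24 | −0.05 |
| 5 | −0.20 | −0.60 | −0.125 |
| 10 | −0.40 | −1.20 | −0.25 |

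A negative shift in the placebo mean makes placebo look better. If an eligible non-user had improved on CDLQI, the sign reverses. These are raw means; the planned MMRM adjusts for baseline, age group and region and will not reproduce them exactly.

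**The case against.** The strongest reply is that the intention is plain. Protocol 9.4.1.3, SAP 5.1.3.5, the narrative of 5.2.2, the per-protocol rule, the disposition listing of rescue users and the sensitivity analyses all point to use, so 5.2.4 merely cites the wrong section. As evidence of intention this stands. It does not settle the text: 5.2.4 cites 5.1.3.4 by number, and three Variable lines repeat the criteria wording.

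For CDLQI the defence goes further. Section 5.2.4 names only IGA 0/1 and PASI 75, and 5.3.4 goes on to speak of rescue rules, so the clear conflict is the Variable line in 5.3.2.2.1. The SAP also plans a treatment-policy estimand (5.3.2.2.2) and a supplementary MMRM on observed data (Table 4). These soften the problem. They do not remove it, because the supplementary analysis drops the treatment failure and rescue rules for everyone, including actual users. Nor does the protocol resolve it: 9.4.1.3 covers the primary endpoints only, and 9.4.1.4 leaves the secondary estimands to the SAP.

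Two stronger readings are tempting. A reader might infer that the co-primary result hangs on which section is programmed; step 3 of the working shows why it almost certainly does not. A reader might also see a contradiction at Week 20. SAP 5.1.3.5 says that "The analysis at and after Week 20 will use the observed data without imputation", while protocol 6.5.1 says that "Participants must discontinue the use of rescue topical steroids by Week 20", so some steroid effect could persist at that visit. The documents do not support calling this an error. Section 5.1.3.5 sets the boundary deliberately and applies treatment failure to steroid use after Week 20. The summaries affected are uncontrolled and descriptive. Exclusion criterion 17, the 2-week topical washout, is an entry condition and not an analysis rule.

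**Conclusion.** The conflict is real in the current text and should be corrected, but its reach is narrow. For the co-primary and other binary endpoints the expected effect is close to nil, and no sample size or power figure is wrong. The exposure is CDLQI: an alpha-controlled endpoint on which an observed change can be replaced by zero with no intercurrent event. The shift is c/25 per placebo participant, 0.20 for an assumed 5-point worsening. If the affected participants are mostly placebo patients who worsened, the error favours placebo and works against guselkumab. CDLQI is last in both the global and the US-FDA sequences, so it cannot alter any other confirmatory test.

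This rests on assumptions that the documents cannot settle: how many eligible participants take no rescue (probably few), their arm, and their CDLQI change.

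**What to change.** In SAP 5.2.4, cite the rescue treatment rules in 5.1.3.5 in place of 5.1.3.4. In the Variable lines of 5.2.2, 5.3.2.1 and 5.3.2.2.1, replace the reference to meeting rescue criteria with *initiates rescue topical steroid before Week 16*. Section 5.3.4 then inherits the corrected rule. Eligible participants who take no rescue keep their observed values, and the primary, per-protocol and sensitivity analyses share one trigger that agrees with protocol 9.4.1.3.

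The cost is SAP wording only, with no new data. The change concerns the analysis definition and leaves the clinical rescue rule and the Week 20 boundary alone. If the Week 16 analysis has already been programmed, state which trigger was used and how many eligible participants in each arm took no rescue.

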5.2.5. Sensitivity Analysis

To assess the robustness of the co-primary endpoint analysis results, two sensitivity analyses will be conducted for the co-primary endpoints as specified below.

Sensitivity Analysis 1

For subjects who have missing IGA or PASI score at Week 16, the score will not be imputed. That is, the Fisher's exact test, stratified by age group and region, will be used for the co-primary endpoints will be performed using observed data after applying treatment failure rules (as defined in Section 5.1.3.2) and rescue treatment rules (as defined in Section 5.1.3.5).

Sensitivity Analysis 2

The second sensitivity analysis will be performed using multiple imputations by fully conditional specification (MI FCS), after applying treatment failure rules (as defined in Section 5.1.3.2) and rescue treatment rules (as defined in Section 5.1.3.5). The missing data of the IGA score of 0/1 and PASI 75 responses will be imputed with FCS logistic regression with treatment group, region, and age group in the model with 500 imputation and seed =36789. The proportion of IGA score of 0/1 and PASI 75 responses at Week 16 will be compared between the guselkumab and the placebo group combining the Mantel-Haenszel estimates stratified by region and age group obtained from the multiple imputation datasets using PROC MIANALYZE.

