#### **Phase 3 Study (CNTO1959PSO3001, VOYAGE 1)**

Study CNTO1959PSO3001 (VOYAGE 1) is a multicenter, Phase 3, randomized, double-blind, placebo- and active-comparator-controlled study in participants with moderate to severe plaque-type psoriasis with 3 parallel treatment groups: placebo, guselkumab 100 mg, and adalimumab. In this study, 837 adult participants were randomized to receive guselkumab (n=329) or adalimumab (n=334) or placebo (n=174). Participants in the placebo group crossed over to guselkumab 100 mg beginning at Week 16.

At Week 16, a significantly greater proportion of participants randomized to guselkumab achieved the co-primary endpoints of an Investigator's Global Assessment (IGA) score of cleared (0) or minimal (1) and Psoriasis Area and Severity Index (PASI) 90 response (85.1% and 73.3%, respectively;  $p < 0.001$  for both endpoints) compared with placebo (6.9% and 2.9%, respectively). At Week 24, a significantly higher proportion of participants achieved an IGA score of cleared (0), an IGA score of cleared (0) or minimal (1), and a PASI 90 response in the guselkumab group than in the adalimumab group. Similar to the observations at Week 24, a significantly higher proportion of participants achieved an IGA score of cleared (0), an IGA score of cleared (0) or minimal (1), and a PASI 90 response in the guselkumab group than in the adalimumab group at Week 48.

Treatment with guselkumab was well-tolerated through Week 48. The frequency of adverse events (AE) was comparable between the guselkumab, placebo, and adalimumab groups through Week 16 and between the guselkumab and adalimumab groups through Week 48. The most common AEs were nasopharyngitis and upper respiratory tract infection. Through Week 16, the percentage of participants with 1 or more serious adverse events (SAEs) was 1.7% (n=3) in the placebo group, 2.4% (n=8) in the guselkumab group and 1.8% (n=6) in the adalimumab group, and was comparable between the guselkumab (4.9% [n=16]) and adalimumab (4.5% [n=15]) groups through Week 48. The incidence of infections was comparable between placebo, guselkumab and adalimumab groups through Week 16, and between the guselkumab group (52.3%) and the adalimumab group (50.2%) through Week 48. No opportunistic infections or active tuberculosis (TB) were reported. No anaphylactic or serum sickness-like reactions were

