### **Phase 3 Study (CNTO1959PSO3002, VOYAGE 2)**

Study CNTO1959PSO3002 (VOYAGE 2) is a multicenter, Phase 3, randomized, double-blind, placebo- and active-comparator-controlled study in participants with moderate to severe plaque-type psoriasis with 3 treatment groups: placebo, guselkumab 100 mg, and adalimumab. In this study, 992 adult participants were randomized to either the placebo (n=248), guselkumab (n=496), or adalimumab (n=248) treatment groups at Week 0. Participants in the placebo group crossed over to guselkumab 100 mg beginning at Week 16. This study evaluated the benefit of maintenance therapy using a randomized withdrawal design starting at Week 28.

At Week 16, a significantly greater proportion of participants randomized to guselkumab achieved the co-primary endpoints of an IGA score of cleared (0) or minimal (1) and a PASI 90 response (84.1% and 70.0%, respectively;  $p < 0.001$  for both endpoints) compared with placebo (8.5% and 2.4%, respectively). In addition, a significantly greater proportion of participants achieved an IGA score of cleared (0), an IGA score of cleared (0) or minimal (1), and a PASI 90 response in the guselkumab group than in the adalimumab group at Week 24.

Treatment with guselkumab was well tolerated. Through Week 16, the proportion of participants experiencing 1 or more AEs was comparable between treatment groups. Nasopharyngitis and upper respiratory tract infection were the most common AEs. The percentage of participants with 1 or more SAEs was comparable between the placebo and guselkumab groups, and slightly higher in the adalimumab group. The incidence of infections was comparable between placebo, guselkumab, and adalimumab groups through Week 16. Through Week 28, the proportion of participants experiencing 1 or more AEs was comparable between the guselkumab and adalimumab groups. Two adalimumab-treated participants reported active TB. No opportunistic infections were reported. No anaphylactic or serum sickness-like reactions were reported and the incidence of injection site reactions was lower in the guselkumab group than the adalimumab group.

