1.4. Sample Size Justification

The assumptions for the sample size calculations for Part 1 of the study are based on the historical response rates from the adults and/or pediatric studies for placebo, guselkumab and the active comparator, etanercept. A power of at least 99% is targeted for the guselkumab versus placebo comparisons for the co-primary endpoints while a power of at least 81% is targeted for the etanercept versus placebo comparisons. Hereby, it is to be acknowledged that etanercept has already been established as an efficacious therapeutic agent for the treatment of pediatric plaque psoriasis. The etanercept active comparator arm is thus included as a "benchmark" (ie, assessment of the efficacy of etanercept compared to placebo is intended to help internally validate the overall results of the pediatric psoriasis study). No formal efficacy comparisons between etanercept and guselkumab will be performed because the relatively small number of participants does not provide sufficient power to detect a difference between these two active treatment groups.

Assumptions for Placebo Response Rates

Across completed adult studies in moderate to severe plaque psoriasis, the placebo response rates for the endpoint of PGA/IGA (0 or 1) have varied between 3.9% and 8.5%, and PASI 75 rates have varied between 3.1% and 8.1% for clinical studies of ENBREL, STELARA, guselkumab, and HUMIRA. In the completed pediatric plaque psoriasis studies (ENBREL, STELARA), the placebo response rates were slightly higher. The PGA responder (0 or 1) rates were 13% and 5.4%, while the PASI 75 rates were 11% and 10.8%, respectively. Note that PGA is a similar measure to IGA which will be used in this study. Therefore, based on consideration of all the available data, an assumption of a 13% placebo response rate for both IGA 0/1 and PASI 75 was utilized for the proposed guselkumab pediatric study.

Assumptions for Guselkumab Response Rates

The IGA responder (0 or 1) rates in the active treatment arm of the adult guselkumab Phase 3 studies (CNTO1959PSO3001 and CNTO1959PSO3002) were 85.1% and 84.1%, respectively, and the PASI 75 rates were 91.2% and 86.3%, respectively. For the proposed pediatric study, a range of the response rates from 65% to 85% for both IGA 0/1 and PASI 75 in the guselkumab treatment group were utilized.

Power for Guselkumab and Placebo Comparisons

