5.1. Analysis Specifications

5.1.1. Level of Significance

All statistical procedures to test superiority hypotheses will be performed at a 2-sided significance level of 0.05. This study is designed to maintain an overall Type I error of 0.05 or less for the co-primary analyses and major secondary analyses. Nominal p-values will be reported for other secondary analyses.

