5.3.5. Sensitivity Analysis

To assess the robustness of the major secondary endpoint analysis results, sensitivity analyses will be conducted as specified in .Table 4

Endpoint	Estimand	Methods
The proportion of subjects who achieve a PASI 90 response at Week 16	Sensitivity analysis 1	Observed data after apply TF and rescue treatment rule
	Sensitivity analysis 2	Multiple imputation with FCS logistic regression (similar to the sensitivity analysis for the primary endpoint with the same seed and the number of imputations)

The proportion of subjects who achieve an IGA score of cleared (0) at Week 16	Sensitivity analysis 1	Observed data after apply TF and rescue treatment rule
	Sensitivity analysis 2	Multiple imputation with FCS logistic regression (similar to the sensitivity analysis for the primary endpoint with the same seed and the number of imputations)
The proportion of subjects who achieve a PASI 100 response at Week 16	Sensitivity analysis 1	Observed data after apply TF and rescue treatment rule
	Sensitivity analysis 2	Multiple imputation with FCS logistic regression (similar to the sensitivity analysis for the primary endpoint with the same seed and the number of imputations)
The change from baseline in CDLQI at Week 16	Sensitivity analysis 1	After apply TF and rescue treatment rule, multiple imputation with Markov Chain Monte Carlo (MCMC) algorithm will be used, which assumes that all the variables in the imputation model have a joint multivariate normal distribution
	Supplementary analysis	MMRM model will be used to test the difference between treatment groups based on observed data. No TF or rescue treatment rule apply.

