5.4.2. Analysis Methods

For US-FDA specific primary and major secondary endpoints, the proportion of participants responding to treatment will be compared between the guselkumab and placebo group in the same manner as the global primary and major secondary endpoints. Table 5 presents the differences between the US-FDA specific primary and major secondary endpoints to the global endpoints. The same endpoints are not listed.

Table 5: Differences between US-FDA specific primary and major secondary endpoints to global endpoints		
	Global endpoints	US-FDA specified endpoints
Co-primary	PASI 75 response at Week 16 is one of the co-primary endpoints.	PASI 90 response at Week 16 is one of the co-primary endpoints.
Major secondary	PASI 90 response at Week 16 is the first major secondary endpoint.	PASI 75 response at Week 16 is the first major secondary endpoint.
Analysis methods	Fisher's exact test, stratified by age group and pooled region, will be used to compare the PASI 90 and PASI 75 response rates between treatment groups.	Same
Sensitivity analyses	
 Observed data after apply TF and rescue treatment rule. Multiple imputation with FCS logistic regression. 	Same

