5.5.2.1.2. Analyses Related to PASI

5.5.2.1.2.1. Through Week 16

- The proportion of participants who achieve a PASI 50 response at Week 16 will be compared between the guselkumab group and the placebo group using Fisher's exact test stratified by region and age. The differences in proportions with exact 95% confidence intervals will be presented.
- The percent improvement from baseline in PASI at Week 16 will be compared between the guselkumab group and the placebo group using a using Wilcoxon rank-sum test.
- The percent improvement from baseline in PASI will be summarized over time through Week 16 by treatment group.
- The proportion of PASI responses (PASI 50, 75, 90, and 100) will be summarized over time through Week 16 by treatment group. Line plots will be provided displaying proportions and exact 95% CIs of PASI 100 responders and PASI 90 responders through Week 16.
- The proportion of PASI responses (PASI 50, 75, 90, and 100) will be summarized over time through Week 16 by treatment group using observed data after applying treatment failure rules and rescue treatment rules.
- The proportion of subjects who achieve 100% improvement, $\geq 90\%$, $\geq 75\%$, or $\geq 50\%$ improvement from baseline in PASI component (induration, erythema, and scaling) and region component (head, trunk, upper extremities, and lower extremities) will be summarized at Week 16 by treatment group.

5.5.2.1.2.2. From Week 16 through Week 52

PASI 90 responders at Week 16 (after withdrawal of guselkumab)

- The time to loss of PASI 90 response after withdrawal will be summarized for participants randomized to the guselkumab group who were PASI 90 responders at Week 16. The percent of subjects who maintained a PASI 90 response from Week 20 through Week 52 will be estimated from life-table methodology and a survival curve (probability that participants maintain PASI 90 response after withdrawn) will be presented.

- The duration of PASI 90 response will be summarized using life-table methodology for participants randomized to the guselkumab group who were PASI 90 responders at Week 16. The estimated number of weeks at which 90%, 75%, 50% and 25% of subjects maintained a PASI 90 response will be provided.

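### Sensitivity Analysis 2 imputes Week 16 response from arm, region and age alone, so it nearly repeats the observed-case analysis, and it has no rule for a placebo arm without responders

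*SAP*

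**What the plan says.** The primary analysis counts a missing Week 16 value as non-response (SAP 5.2.4). SAP 5.2.5 adds two checks on the co-primaries, both run after the treatment-failure and rescue rules.

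- **Sensitivity Analysis 1** leaves missing scores missing and applies the stratified Fisher's exact test to observed data.
- **Sensitivity Analysis 2** uses multiple imputation, with missing responses "imputed with FCS logistic regression with treatment group, region, and age group in the model with 500 imputation and seed =36789". Mantel-Haenszel estimates over region and age group are then combined across imputations.

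Table 4 (SAP 5.3.5) carries this to PASI 90, IGA 0 and PASI 100: "Multiple imputation with FCS logistic regression (similar to the sensitivity analysis for the primary endpoint with the same seed and the number of imputations"). Table 5 (SAP 5.4.2) keeps the same sensitivity analyses for the US-FDA set, in which "PASI 90 response at Week 16 is one of the co-primary endpoints".

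PASI and IGA are also scheduled at Weeks 4, 8 and 12 (Protocol 1.3.1), and the SAP uses those visits descriptively: "The proportion of PASI responses (PASI 50, 75, 90, and 100) will be summarized over time through Week 16 by treatment group" (SAP 5.5.2.1.2). They are not listed in the imputation model. Neither document mentions separation, zero cells, an augmented or penalised likelihood, or a fallback.

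**The concern.** There are two separate problems.

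1. **Co-primaries.** A missing value is drawn from roughly the observed rate in that patient's arm and stratum, and the analysis then averages over those strata. This reproduces the observed-case estimate with some added noise. Earlier scores, which could separate likely responders from likely non-responders among the missing patients, are left out. Two stated robustness checks then amount to little more than one.

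2. **Sparse endpoints.** If no observed placebo patient responds and at least one placebo value is missing, the fitted placebo log-odds run to minus infinity and their standard error grows without limit. Draws from that fit depend on where the iterations stop. For a US-FDA co-primary, the reported sensitivity result could then be set by a software default.

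**Working it through.** **Inputs from the documents.** Guselkumab n=40 (30 in Part 1a, 10 in Part 1b) and placebo n=25 (15 and 10), with planning rates of 65% and 13% (SAP 1.4). Adult placebo PASI 90 is the second figure in each pair in Protocol 2.2.1: VOYAGE 1 "compared with placebo (6.9% and 2.9%, respectively") and VOYAGE 2 "compared with placebo (8.5% and 2.4%, respectively").

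**Assumed.** The Week 16 missing rate (4-10%, and up to 15% in one set), an even region split, the correlation between Week 12 and Week 16, and placebo rates for IGA 0 and PASI 100.

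**Plan's own figure.** The unstratified two-sided Fisher's exact test gives 99.3% power at 65% vs 13% with 40 vs 25. For etanercept (53/55/60%, 25 vs 25) it gives 81.0/84.9/92.4%. Both agree with SAP Tables 1 and 2.

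**Step 1: near-duplication (65% vs 13%).** Mean absolute gap between the planned imputation and the observed-case Mantel-Haenszel difference:

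| Missing | Completely at random | Dependent on earlier response |
|---|---|---|
| 5% | 0.4 points | 0.5 points |
| 10% | 0.7 points | 0.8 points |
| 15% | 1.0 points | 1.1 points |

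The effect is 65 - 13 = 52 points, with a standard error of about 10 points (0.098 observed-case, 0.099 imputed, at 5% missing). Further simulations gave 0.4-0.7 points at 5-10% missing, with correlation 0.996-0.999 between the two estimates. The largest gap in any single simulated trial was 6.8 points.

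**Step 2: what earlier scores add.** This is the root mean squared error against the full-data estimate, with missingness made likelier in patients doing worse at Week 12.

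- Adding a Week 12 score (correlation 0.70-0.85 with Week 16) lowers it from 2.4 to 1.7-2.0 points at 5% missing, and from 3.2-3.3 to 2.4-2.9 at 10%.
- A binary Week 12 response gains at most about 0.2 points.
- In a repeat run the planned model gave 2.3-2.6 and about 3.4. All six scores (PASI and IGA at Weeks 4, 8 and 12) gave about 2.0 and 2.6-3.0.

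**Step 3: chance of the zero cell.** With placebo rate p and missing rate m:

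- P(0 of 25) = (1-p)^25
- P(no observed responder and at least one missing) = (m + (1-m)(1-p))^25 - ((1-m)(1-p))^25

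For p = 0.024 and m = 0.04 the second is 0.97696^25 - 0.93696^25 = 0.558 - 0.196 = 0.362.

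| p | Basis | P(0 of 25) | Joint, m = 4% to 8% |
|---|---|---|---|
| 2.4% | adult PASI 90 | 54% | 36-50% |
| 2.9% | adult PASI 90 | 48% | 32-45% |
| 5% | assumed | 28% | 19-27% |
| 10% | assumed | 7% | 5-8% |
| 13% | IGA 0/1 and PASI 75 planning rate | 3% | not computed |

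The joint event concerns observed patients, so it can slightly exceed P(0 of 25).

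**Step 4: what the fit then does.** With zero observed placebo responders, an unpenalised fit imputes missing placebo patients as responders about 10% of the time after 5 Newton steps, 32% after 8, 47% after 12 and 50% after 20. An augmented likelihood gives 4-5%. In a constructed data set (guselkumab 28/40, placebo 0/25, etanercept 8/25) the placebo log-odds reached -26 with a standard error of about 100,000. About half of the missing placebo values were imputed as responders, against 7-10% with a penalised fit.

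**Step 5: effect on the result.** With 3 placebo and 4 guselkumab values missing:

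| Guselkumab response | Augmented | Diverged |
|---|---|---|
| 70% | 0.697 (SE 0.080) | 0.642 (SE 0.109), z = 5.9 |
| 30% | 0.294 (SE 0.081), z = 3.6 | 0.237 (SE 0.109), z = 2.2 |

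All remain significant at the two-sided 0.05 level.

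**The case against.** The strongest points on the other side, and what remains of each:

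- **The SAP does not say these are the only model terms.** True, but it lists three and no others, and an analyst following the text would fit those three. Reading earlier visits into it needs words that are not there.
- **Sensitivity Analysis 1 is a Fisher test, not a Mantel-Haenszel estimate.** This stands as a limit: the p-values come from different methods, and the near-duplication concerns the effect estimate and its standard error.
- **Both checks still vary the primary assumption.** This also stands. Non-responder imputation differs from observed cases by 2.8, 5.2 and 7.7 points at 5, 10 and 15% missing. The complaint is that the second check adds little to the first.
- **Treatment-failure and rescue rules act first.** They remove many patients doing badly, and the simulations did not model them. Residual missingness may be lower and less informative than assumed.
- **Adult rates overstate the zero cell.** The SAP says that in paediatric studies "the placebo response rates were slightly higher" (for PGA 0/1 and PASI 75), so the 5% and 10% rows may be nearer the truth.
- **The stopping points are arbitrary.** Agreed. They show that the answer is undetermined; they do not predict what the sponsor's software will report.
- **Little turns on it.** With no placebo responders, superiority is hardly in doubt at any substantial guselkumab response. This limits the importance of the point but leaves the gap in the specification.

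**Conclusion.** The concern holds, as a low-cost improvement and not as a threat to the trial's conclusions. For IGA 0/1 and PASI 75, Sensitivity Analysis 2 differs from an observed-case estimate by about half a point on average at 5-10% missing, so it is close to redundant. For PASI 90, IGA 0 and PASI 100 the plan does not specify what happens when no placebo patient responds. For PASI 90 that event, with at least one placebo value missing, has probability 32-50% at adult rates and 5-8% at an assumed 10% rate.

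The two parts describe different situations. With responders and non-responders in both arms, the second analysis copies the first; with an empty placebo cell it can depart from it, but only as an artefact. That artefact shrinks the guselkumab effect, inflates the standard error, and reversed no conclusion with 1-3 missing placebo values. The primary test, its power and the testing sequence are unaffected. The sizes rest on assumed missing rates, visit correlations and paediatric placebo rates; the two mechanisms do not.

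**What to change.** Amend SAP 5.2.5, with matching wording in Table 4 and Table 5:

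1. Add the PASI and IGA scores at Weeks 4, 8 and 12, after the treatment-failure and rescue rules, to the imputation model. Alternatively, impute the Week 16 scores and derive the responses from them. Use scores, not binary PASI 90, PASI 100 or IGA 0 indicators, which would add empty cells and worsen separation.
2. Name an augmented or penalised likelihood for any logistic imputation step used for PASI 90, IGA 0 and PASI 100.

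Adopt both together, because more predictors with about 25 placebo patients make a stabilised likelihood more necessary. The cost is SAP wording and a few lines of code. No new data are needed, and the primary analysis does not change.
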